## Statistical Analysis Plan Template

Sponsor:	ProQR Therapeutics		
Protocol:	PQ-110-002		
Document Version No.:	1.0	Document Date:	04 JAN 2022

If a partial medication start date is consistent with occurring on Day 1, the subject received study treatment, and the available medication end date information indicates that the medication did not end before Day 1, the imputed medication start date will be Day 1.

Otherwise, if the medication start date is partially recorded, the medication start date will be imputed as follows:

- The first day of the month if day is missing
- January if month is missing
- If only year is recorded, 1 January

If medication start date imputed in this way is before the date of the subject's informed consent, the medication start date will be re-imputed as the date of the informed consent.

### 4.2.9.4.2. *Partial and Missing End Dates for Concomitant Medications*

If the end date for a medication is completely missing, the end date will be imputed as the date of the subject's last visit. If the end date for a medication is partially recorded, the medication end date will be imputed as follows:

- The last day of the month if day is missing
- December if month is missing
- If only year is recorded, 31 December

If a medication end date imputed in this way is after the date of the subject's last visit, the medication end date will be re-imputed as the date of the subject's last visit.

### 4.2.10. **Visit Windows**

All visits should occur at the scheduled visits according to the schedule of events (Section 2.4), but unscheduled visits may be necessary and visits to be performed at scheduled time points may be

## Statistical Analysis Plan Template

Sponsor:	ProQR Therapeutics		
Protocol:	PQ-110-002		
Document Version No.:	1.0	Document Date:	04 JAN 2022

performed later or earlier than planned in the protocol. All data to be summarized over time will be tabulated by visit, based on the schedule of events.

The Screening/ Day 1 visit should be the last visit of study PQ-110-001, ie, all Screening/Day 1 assessments should take place during the EOS visit of study PQ-110-001. If these visits do not occur at the same time, a separate Screening/Day 1 visit should be performed as part of PQ-110-002. Dosing visits occur on Day 1 for the contralateral eye and then every 6 months. Dosing visits for the previously (first) treated eye will occur 3 months after the dosing visit for the contralateral eye and then every 6 months. Study center phone calls to the subjects will occur 7 days post-IVT injection,  $\pm$ 3 days. The End of Study (EOS) visit occurs 3 months after the last dose of study drug for a subject.

For each visit, a visit window will establish a time interval around which data from the scheduled visit and any unscheduled visits will be considered to determine which data within the visit window should be summarized. In general, the visit window is the scheduled visit day +/-30 days. In exceptional cases, eg. related to the significant restrictions in site activities or subject's ability to travel to sites for visits as occurring related to the COVID-19 pandemic, extensions of the visit window or alterations in the schedule of event can be approved by the Medical Monitor. Such extensions of the visit window will be documented as protocol deviations. Still, sites should make every reasonable effort to complete scheduled visits within the time windows defined in the protocol.

Actual dates and times will be used for pharmacokinetic analyses rather than nominal days and times.

### 4.3. Interim Analyses

Ongoing review of safety and efficacy data will be conducted to inform the program. Interim analyses may be performed, eg, yearly, or at key time points during clinical development.

### 4.4. Subject Disposition

A tabulation of subject disposition will be presented by treatment group, age category and all subjects combined. Subject disposition will be summarized for All Screened Subjects, including the number

## Statistical Analysis Plan Template

Sponsor:	ProQR Therapeutics		
Protocol:	PQ-110-002		
Document Version No.:	1.0	Document Date:	04 JAN 2022

screened, the number screened failure, the number who received study drug in the first treated eye and contralateral eye, the number in each subject population for analysis, the number that discontinued study drug, and the number that discontinued the study, and the reasons for study discontinuation.

The same disposition summary described above will be also provided for the Safety Population.

A by-subject listing of study completion information, including the reason for premature study discontinuation, will be presented.

### 4.5. Drug Exposure

The summary of exposure to study drug will be presented by treatment group for the Safety Population.

The exposure summary will summarize administration of study treatment to the first treatment eye, and the contralateral eye. The summary will include the number of doses received, the duration of treatment, the duration of follow up post first dose, the duration of follow-up post last dose, the cumulative dose, and the average daily dose, which will be calculated as follows:

- Duration of Treatment = date of last dose-date of first dose+1
- Total Duration of Follow Up Post First Dose = date of last assessment - date of first dose+1
- Duration of Follow Up Post Last Dose = date of last assessment – date of last dose+1
- Cumulative Dose = sum of all doses received
- Average Daily Dose = cumulative dose ÷ duration of follow up post first dose

The number of doses received will be summarized as a categorical variable, with the following categories, and the categories may be changed as per the available data:

- 1, 2, 3, 4, 5, 6 or 7 doses for summaries of exposure in the treatment eye
- 1, 2, 3, 4, 5, 6 or 7 doses for summaries of exposure in the contralateral eye

Listings of study drug exposure and compliance will be provided based on the Safety Population.

## Statistical Analysis Plan Template

Sponsor:	ProQR Therapeutics		
Protocol:	PQ-110-002		
Document Version No.:	1.0	Document Date:	04 JAN 2022

### 4.6. Demographic and Baseline Characteristics

Subject demographics and baseline 001 and 002 characteristics information for the Safety Population will be summarized by treatment group, age category and all subjects combined using descriptive statistics. No formal statistical comparisons will be performed.

Subject characteristics at baseline include age (as recorded on the eCRF), age category (<18 years,  $\geq$ 18 years older), gender, race, ethnicity, body weight, height and Body Mass Index (BMI) as well as genotype for *CEP290* c. 2991+1655A>G (homozygous, compound heterozygous). The following formulae will be used to calculate BMI:

Body Mass Index (BMI)= kg/m^2 (where kg is a person's weight in kilograms and m^2 is height in meters squared)

Baseline 001 and 002 disease characteristics include ophthalmic examinations, measurements and tests and BCVA (logMAR) (with separate categories for BCVA based on the Holladay and on the Lange equivalency table, in case of subjects for whom BCVA values could only be obtained via the clinical practice assessment).

Demographic and baseline characteristics data will also be provided in a by subject data listing.

A summary of non-ocular medical history and ocular medical history will be provided for the Safety Population. Non-ocular and ocular medical history will be coded to system organ class (SOC) and preferred term (PT) using the Medical Dictionary for Regulatory Activities (MedDRA) Version 20.0. Non-ocular and ocular medical will be summarized separately, by treatment group and for all subjects combined, SOC and PT. If a subject has multiple non-ocular or ocular history records which are coded to the same PT within the same SOC, that PT for that subject will only be reported once. The same applies if a subject has multiple non-ocular or ocular history records which are coded to the different PTs within the same SOC, that SOC will only be reported once for that subject.

## Statistical Analysis Plan Template

Sponsor:	ProQR Therapeutics		
Protocol:	PQ-110-002		
Document Version No.:	1.0	Document Date:	04 JAN 2022

Ocular and non-ocular medical history will also be listed separately using by-subject listings which will include medical and surgical history, date of onset and the date of resolution or ongoing status.

### 4.7. Safety Analyses

All reporting of safety data will be based on the Safety Population. Listings will include all available data.

#### 4.7.1. Adverse Events

Adverse events will be coded using the Medical Dictionary for Regulatory Activities (MedDRA) Version 20.0 and displayed in tables and listings using System/Organ/Class (SOC) and Preferred Term.

Adverse events are summarized by subject frequencies, therefore, in any tabulation, a subject contributes only once to the count for a given adverse event (SOC or preferred term).

A treatment emergent adverse event (TEAE) is defined as an event that was not present prior to administration of the first dose of study drug and present after the first dose or if it represents the exacerbation of an event that was present prior to the first dose.

The number and percentage of subjects with any TEAE, with any TEAEs assessed by the Investigator as related to study drug and those related to drug administration (definite, probable, or possible relationship), and with any serious adverse event will be summarized by treatment group and overall. Deaths, TEAE severity, seriousness, outcomes (resolved, resolved with sequelae, not resolved, resolving, fatal and unknown) and study discontinuation due to TEAE will also be tabulated by treatment group. In these tabulations, each subject will contribute only once (i.e., the most related occurrence or the most severe occurrence) to each of the counts in the descriptive analysis, regardless of the number of episodes. No formal hypothesis-testing analysis of adverse events will be performed.

Missing or partial start and end dates will be imputed as described in Section 4.2.9.3 before determining whether an AE is treatment emergent. For subjects with an actual or imputed AE start date on Day 1, the

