### 7.2 Dosing and Follow-up Visits

Dosing visits occur on Day 1 for the contralateral eye and then every 6 months. Dosing visits for the previously (first) treated eye will occur 3 months after the dosing visit for the contralateral eye and then every 6 months.

This between-eye interval could be adapted in agreement with the Medical Monitor if safety data are supportive, and for logistic reasons.

Study drug will be administered by qualified ophthalmologists via IVT injection. If sedation or anesthesia is performed during the administration of the IVT injection, general health monitoring should be provided by the study anesthesiologist pre and post sedation/anesthesia, according to local institutional guidelines. Subjects should be monitored for increases in IOP and signs of inflammation and endophthalmitis during the post-injection period.

Study center phone calls to the subjects will occur 7 days post-IVT injection,  $\pm 3$  days.

All follow-up study visits, assessments and procedures should be completed as indicated in the SOE. However, if no dosing occurs at a visit; the +1D post dose visit and the +7D post dose phone call may be skipped at the discretion of the Investigator.

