### **10.6 Safety Analyses**

#### **10.6.1 Treatment Emergent Adverse Events**

A treatment emergent adverse event (TEAE) is defined as an event that was not present prior to administration of the first dose of study drug and present after the first dose or if it represents the exacerbation of an event that was present prior to the first dose.

Adverse events noted during the study will be coded to system organ classes (SOCs) and preferred terms (PTs) using the Medical Dictionary for Regulatory Activities (MedDRA) dictionary. The overall incidence of TEAEs will be summarized by dose group and classified by SOC and PT. Deaths, AE severity, seriousness, relationship to study drug and study discontinuation due to AE will also be tabulated by dose group. An AE will be considered drug-related if the Investigator indicated the event is at least “possibly” related or if the relationship is missing. Adverse events with missing start dates, but with stop dates overlapping into the treatment period will be counted as treatment emergent. All AEs will be listed in subject listing and summarized by numbers and percentages of subjects by dose for each portion of the study separately. If a subject reports the occurrence of a particular event more than once, the most severe of those events will be included in the summary tables of TEAEs, and the most severe of the treatment-related events will be included in the summary tables of TEAEs.

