### 2.5. Safety, Efficacy and Pharmacokinetic Endpoints

#### 2.5.1. Safety Endpoints

##### 2.5.1.1. Primary Endpoint

The primary endpoints are:

- Frequency and severity of ocular AEs
- Frequency and severity of non-ocular AEs

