## Statistical Analysis Plan Template

Sponsor:	ProQR Therapeutics		
Protocol:	PQ-110-002		
Document Version No.:	1.0	Document Date:	04 JAN 2022

Unless otherwise stated, the following summaries of TEAEs will be presented for all non-ocular TEAEs, and separately for ocular TEAEs in the first treated eye , in the treated contralateral eye before the first dose in the study , in the treated contralaertal eye after the first dose in the study and in the non-treated contralateral eye. Unless otherwise stated, any summary of any type of TEAEs or serious adverse events (SAEs) which includes the SOC and PT of the events, will order the SOC and the PTs within the SOC in alphabetical order.

The tables that provide an overview of TEAEs will be presented by treatment group, to include the number (and percentage) of subjects who had any TEAE, SAE, TEAE leading to discontinuation from study treatment, TEAE leading to discontinuation from the trial, deaths and will summarize the number of subjects who had a TEAE by severity, by relationship to study treatment and by relationship to study treatment administration.

The adverse events that were identified by the Investigator as meeting the definition of an adverse event of special interest (AESI), as defined in Section 9.2.4 of the clinical study protocol will be supplemented by events for which an AESI has been defined but for which are not meeting the criterion for an AESI.

The following summary tables will be produced:

- Overview of Non-ocular TEAEs
- Overview of Ocular TEAEs
- Non-ocular TEAEs by, SOC and PT
- Treatment-emergent AESIs
- Non-ocular TEAEs by Severity
- Ocular TEAEs by Severity
- Non-ocular TEAEs by Relationship to Study Treatment
- Ocular TEAEs by Relationship to Study Treatment
- Non-Ocular TEAEs by Severity and Relationship to Study Treatment
- Ocular TEAEs by Severity and Relationship to Study Treatment

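### Adverse event frequency, part of the primary endpoint, is planned only as a once-per-subject percentage, in eye and period categories whose time at risk can differ widely

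*SAP*

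**What the plan says.** The ocular part of the primary endpoint is "Frequency and severity of ocular AEs" (SAP 2.5.1.1); non-ocular events have a matching entry. SAP 4.7.1 gives the counting rule: "Adverse events are summarized by subject frequencies, therefore, in any tabulation, a subject contributes only once to the count for a given adverse event". Its overview tables are "to include the number (and percentage) of subjects who had any TEAE, SAE, TEAE leading to discontinuation from study treatment", and so on. Protocol 10.6.1 has the same measure: "All AEs will be listed in subject listing and summarized by numbers and percentages of subjects by dose for each portion of the study separately". No formal testing of adverse events is planned.

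Ocular treatment-emergent events are summarized separately for four categories: the first treated eye; the contralateral eye that goes on to be treated, "in the treated contralateral eye before the first dose in the study"; that same eye after its first dose; and the contralateral eye that is never treated.

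On timing, Protocol 7.2 says "Dosing visits occur on Day 1 for the contralateral eye and then every 6 months", and "Dosing visits for the previously (first) treated eye will occur 3 months after the dosing visit for the contralateral eye and then every 6 months". Under Protocol 4.2, whether and when to start the contralateral eye is decided subject by subject. Protocol 7.3 puts the end-of-study visit 3 months after the last dose. The Protocol synopsis sets no fixed end to the study.

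SAP 4.5 tabulates exposure per eye in dose categories from 1 to 7, which may be changed to suit the data. Its follow-up measure is "Total Duration of Follow Up Post First Dose = date of last assessment - date of first dose+1". Nothing links these durations to the adverse event tables. Neither document plans a rate per eye-year, a rate per injection or a time-to-first-event analysis. Protocol 10.1 allows an optional analysis by 3- or 6-month intervals, which SAP 4.7.1 does not take up.

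**The concern.** A percentage of subjects with at least one event rises with the time they are watched, even if the underlying rate never changes. Splitting ocular events into before and after dosing, and into treated and non-treated eyes, invites the reader to compare those categories. If they cover different lengths of time, part of any difference is an artefact of time at risk. The same applies between subjects with few and many doses, and between successive interim cuts: in a fixed group a cumulative percentage can only stay level or rise.

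The once-only rule also leaves out of the summary tables any recurrence after a later injection. Protocol 9.4.3.2 has recurrences recorded individually, so the data exist. Protocol 2.3.1 gives safety as a reason to keep the number of injections low, so how often events return with repeat injection is a question this study should address.

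**Working it through.** The documents state no adverse event rate and no exposure-adjusted figure, so there is nothing to reproduce. The check derives time at risk from the schedule and then shows what time alone does to the percentage.

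**1. Time after an eye's first dose.** Inputs: 6-month interval (Protocol 7.2), end of study 3 months after the last dose (Protocol 7.3), 1 to 7 doses (SAP 4.5). For k doses, follow-up = 6(k − 1) + 3 months.
- k = 1: 3 months.
- k = 7: 36 + 3 = 39 months, a 13-fold range.

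**2. The two treated eyes on plan.** With k doses in each eye, the contralateral eye is dosed at months 0, 6, …, 6(k − 1) and the first treated eye at months 3, 9, …, 6(k − 1) + 3. End of study falls at 6(k − 1) + 3 + 3 = 6k months. Follow-up is then 6k months for the contralateral eye and 6k − 3 months for the first treated eye, counted from its first dose in this study. At k = 7 that is 42 against 39 months. The contralateral pre-dose period is about zero on plan, and has no upper limit if the start is delayed.

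**3. Effect of time on the percentage.** Assume one constant rate r per eye-year in every category. The expected share of eyes with at least one event by t years is 1 − exp(−r·t).

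| Assumed r | 3 months (t = 0.25) | 39 months (t = 3.25) |
|---|---|---|
| 0.1 | 1 − exp(−0.025) = 2.5% | 1 − exp(−0.325) = 28% |
| 0.3 | 1 − exp(−0.075) = 7% | 1 − exp(−0.975) = 62% |
| 0.5 | 1 − exp(−0.125) = 12% | 1 − exp(−1.625) = 80% |

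Time alone moves the percentage by a factor of about 7 (80/12) to 11 (28/2.5) between these extremes.

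**4. The same illustration as a rate.** With 11 eyes and r = 0.3, the denominators are 11 × 0.25 = 2.75 and 11 × 3.25 = 35.75 eye-years. Expected events are 0.3 × 2.75 = 0.825 and 0.3 × 35.75 = 10.725. Events divided by eye-years gives 0.3 in both columns.

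**5. Precision.** Exact (Clopper-Pearson) 95% intervals with 11 eyes: 1/11 gives 0.2% to 41.3%; 7/11 gives 30.8% to 89.1%.

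**6. Whether existing exposure data suffice.** The durations in SAP 4.5 all run from a first or last dose. They serve the first treated eye and the contralateral eye after dosing. They give no observation time for the contralateral eye before its first dose or for the never-treated eye, which are two of the four categories.

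**7. Capture of events in those two categories.** Protocol 9.4.1 starts adverse event capture for the contralateral eye at that eye's first dose, yet SAP 4.7.1 tabulates earlier contralateral events and events in eyes never dosed. A treatment-emergent event before an eye's first dose also fits the definition only if the first dose means the subject's first dose in either eye. Low counts there could reflect non-capture as well as short observation.

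**The case against.** The best defence is that this is a descriptive, uncontrolled extension in at most 11 subjects. The eye and period summaries are presented separately, with no test between them. Severity is part of the endpoint and has its own tables. Doses and follow-up are reported per eye in the exposure table, and all events are listed, so recurrences can be found. Treated versus non-treated eyes are also subject to case-by-case selection, which no exposure adjustment removes. These points stand, and they limit the concern to the frequency component and to the summary tables.

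Three stronger readings are tempting and go too far. A reader might infer that the two treated eyes are followed for very unequal times; on plan they differ by about 3 months. A reader might infer that the primary endpoint merely measures follow-up; severity is also part of it, and only the frequency component is confounded. A reader might take the illustration as a finding that the true rate is equal in every category; that is an assumption. A constant rate is itself doubtful where events cluster around injections. The contrast of 3 with 39 months also compares extremes, since no actual follow-up lengths are given.

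The defence does not answer the main point. The separate exposure table cannot supply a denominator for two of the four categories, and listings do not replace a summary of a primary endpoint.

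**Conclusion.** The concern holds in limited form. The frequency component of the primary endpoint is planned only as a once-per-subject percentage across categories whose time at risk can differ widely, and neither document adjusts for exposure. The imbalance lies in the contralateral pre-dose against post-dose periods, in delayed contralateral starts, and in few against many doses. Between the extremes of the schedule, time alone could take the expected percentage from 2.5% to 28% at the lowest assumed rate and from 12% to 80% at the highest. This rests on assumed constant rates, and on the SAP's dose categories and the 6-month schedule being followed; it is not a forecast. Adding rates is a worthwhile, inexpensive improvement to an analysis that stays descriptive.

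**What to change.** 1. In SAP 4.7.1, define the start and end of observation for each of the four eye and period categories. State whether the first treated eye's time includes PQ-110-001.
2. Reconcile Protocol 9.4.1 and the treatment-emergent definition with the SAP's pre-dose and never-treated contralateral categories. If those events were not fully captured, report no rate there: dividing an incomplete count by full eye-years would give a falsely low figure.
3. In the overview and special-interest event tables, keep n (%) and add the number of distinct events, eye-years (subject-years for non-ocular events), and events per eye-year with exact intervals. Protocol 9.4.3.2 has a persistent event entered again when it worsens, so collapse such entries to one event and count true recurrences separately.
4. Add events per injection for treated eyes after dosing only; the measure is undefined in the other two categories.

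The cost is some programming plus the definitional work in steps 1 and 2. The downside is wide intervals with at most 11 subjects. Repeat events within an eye are also correlated, so the intervals should be read as descriptive.
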